### **Option 2: A 48-week cohort study with scheduled study visits**

#### **Baseline visit (Visit 1), study week 0**

1. Informed consent obtained
2. Eligibility determined based upon inclusion and exclusion criteria
3. Brief physical examination (by RN) including height and weight performed
4. Medical history obtained

5. Urine pregnancy testing
6. Administer Demographic questionnaires
7. Asthma control evaluation (Asthma Control Questionnaire and Asthma Control Test)
8. Administer PROMIS symptom questionnaires
9. Measure exhaled nitric oxide
10. Perform spirometry with oscillometry (with bronchodilator reversibility)
11. Perform venipuncture for:
  - a. Total IgE (Children's Healthcare of Atlanta)
  - b. Inhalant allergen specific IgE (Children's Healthcare of Atlanta)
  - c. Complete blood count with differential (Children's Healthcare of Atlanta)
  - d. Plasma and white blood cells for aim 3 ([name] laboratory)
12. Perform sputum induction with samples stored for aim 3 ([name] laboratory)
13. Triamcinolone acetonide injection

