**Steroid Responsiveness visit (Visit 2), Study Week 2 (window +7 days)**

1. Brief physical examination (by RN) including height and weight performed
2. Medical history obtained
3. Urine pregnancy testing
4. Asthma control evaluation (Asthma Control Questionnaire and Asthma Control Test)
5. Administer PROMIS symptom questionnaires
6. Measure exhaled nitric oxide
7. Perform spirometry with oscillometry (with bronchodilator reversibility)
8. Perform venipuncture for:
  - a. Complete blood count with differential (Children's Healthcare of Atlanta)
  - b. Plasma and white blood cells for aim 3 ([name] laboratory)
9. Perform sputum induction with samples stored for aim 3 ([name] laboratory)

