**Follow-up visits (Visits 3 and 4), Study Week 16, 32 (window +4 weeks)**

1. Brief physical examination (by RN) including height and weight performed\*
2. Medical history obtained
3. Urine pregnancy testing\*
4. Asthma control evaluation (Asthma Control Questionnaire and Asthma Control Test)
5. Administer PROMIS symptom questionnaires
6. Measure exhaled nitric oxide\*
7. Perform spirometry with oscillometry\*

\*procedure will not be performed if follow-up occurs by telephone

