### **Plan for supplemental R01 funding (aims 4-5)**

Aim 4 will determine associations between neighborhood air quality indices (predictor variables) and patient-reported asthma control and symptoms, lung function, exacerbation rates and QOL (outcome variables) during two separate seasons (spring/summer versus fall/winter) in children stratified by high- versus low-to-moderate social vulnerability. Prespecified outcomes are continuous and will be evaluated with linear regression. Analyses will be stratified by social

vulnerability (high versus low-to-intermediate) and season (spring/summer versus fall/winter). Models will be generated for air quality variables on the visit date and for each of the five lag days prior to the visit. Given the relatively small number of participants and high number of air quality predictor variables, we will use ElasticNet to select the most important variables in Python. Variables with a Pearson correlation coefficient  $>0.8$  will be removed to minimize redundancy. Models will be evaluated considering pertinent covariates such as age, asthma medications and tobacco smoke exposure. To further address sex as a biological variable, models will also be fitted by sex, with statistical comparison of results observed in boys and girls. Analyses will assume a type 1 error rate of 0.05 without adjustments for multiple testing (exploratory study). For exploratory dichotomized outcomes that are not pre-specified, such as exacerbation occurrence or QOL scores below a threshold, partial least squares regression and discriminant analysis could be performed to determine the air quality features that provide the largest separation between outcomes. Temporal stability of the results would be assessed by repeating analyses during the second season.

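### Aim 4 names only linear regression within season and does not say which visits of a child enter or how within-child correlation is handled, so the stated 0.05 type 1 error is not assured

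*Combined protocol and SAP*

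**What the plan says.** Section U, plan for aims 4-5, gives one model for Aim 4: "Prespecified outcomes are continuous and will be evaluated with linear regression". The outcomes listed are asthma control and symptoms, lung function, exacerbation rates and quality of life. Analyses are stratified by social "vulnerability (high versus low-to-intermediate) and season (spring/summer versus fall/winter"). On exposure: "Models will be generated for air quality variables on the visit date and for each of the five lag days prior to the visit". On the error rate: "Analyses will assume a type 1 error rate of 0.05 without adjustments for multiple testing (exploratory study"). On the other season: "Temporal stability of the results would be assessed by repeating analyses during the second season". Nothing states which visits of a child enter a season's model. No random effect, GEE or clustered variance is named.

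Section K sets the Option 2 visits: "Baseline visit (Visit 1), study week 0"; "Steroid Responsiveness visit (Visit 2), Study Week 2 (window +7 days"); "Follow-up visits (Visits 3 and 4), Study Week 16, 32 (window +4 weeks"); and a final visit at week 48, also with a 4-week window. Visits 3 to 5 may be done by telephone, in which case spirometry is skipped. Option 1 children have questionnaire contacts at weeks 24 and 48 after their single visit.

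The plan for aims 1-3, in the same Section U, names GEE for quality of life over visits 3, 4 and 5, and linear mixed effects models for the biomarker data.

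**The concern.** Exposure is dated by visit, so the natural data row for the visit-measured outcomes is a visit. Section K gives each Option 2 child up to five visits for only two season labels. Two visits of one child share that child's underlying severity, and may share the air quality of the child's neighborhood. Ordinary linear regression assumes independent rows. If several visits per child are pooled under it, the reported standard errors, and therefore the 0.05 threshold, need not be right.

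Visit 2 raises a further question. It is timed 14-21 days after the triamcinolone injection in order to measure the steroid response. The Aim 4 text neither excludes nor flags it. A child followed by telephone has lung function only at visits 1 and 2, one before the injection and one after, and usually in the same season.

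At stake is whether an Aim 4 association at p < 0.05 means what the plan says it means. The primary and secondary outcomes are not affected.

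**Working it through.** The documents give no sample size, power or standard error for Aim 4, so there is no stated figure to reproduce.

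**Step 1. Visits per season label.** Inputs: Option 2 visits at weeks 0, 2, 16, 32 and 48 (Section K) and two season labels (Section U). Calendar dates of the seasons are not given. I assumed half-years starting 1 March, 20 March or 1 April and counted over all 365 start dates; all three gave the same results.

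- Five visits under two labels put at least three under one label. At nominal weeks the maximum is three for 62% of start dates and four for 38%. At the late end of the windows it is 51% and 49%.
- Visits 1 and 2 alone share a label for 92% of start dates.
- Without visit 5, the maximum under one label is two for 46% of start dates and three for 54%.
- Without visit 2, it is two for 54.5% and three for 45.5%.
- Visits 1 and 5 are 48-52 weeks apart. If a season means one continuous period, not a label across years, at most two visits fall together for 61% of start dates (77% at late windows).
- Option 1 data at weeks 0, 24 and 48 always put at least two under one label.

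**Step 2. Effect of pooling on the error rate.** Let m be the visits per child, ρy the within-child correlation of the outcome and ρx that of the exposure. With no true effect, the true variance of the regression slope divided by the variance that ordinary regression reports is approximately

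V = 1 + (m − 1) × ρx × ρy,

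and the actual two-sided error rate at nominal 0.05 is 2 × [1 − Φ(1.96/√V)]. The documents give none of these values. I assumed m = 3, ρy = 0.6, 40 children per stratum and a two-sided test.

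| Exposure correlation ρx | V | √V | Error rate |
|---|---|---|---|
| −0.5 (varies only within child) | 1 − 2×0.5×0.6 = 0.40 | 0.63 | 0.2% |
| 0 | 1.00 | 1.00 | 5.0% |
| 0.2 | 1 + 2×0.2×0.6 = 1.24 | 1.11 | 7.8% |
| 0.4 | 1.48 | 1.22 | 10.7% |
| 0.6 | 1.72 | 1.31 | 13.5% |
| 0.8 | 1.96 | 1.40 | 16.2% |
| 1 (constant within child) | 1 + 2×1×0.6 = 2.20 | 1.48 | 18.6% |

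Simulation of 40 children with three visits each agrees: about 5-6% at ρx = 0, about 8% at 0.2, about 19% at 1, and 0.2% when exposure varies only within child. With two visits per child and exposure constant, V = 1 + 0.6 = 1.60 and the error rate is about 12%.

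**Step 3. Sensitivity to the outcome correlation.** With 74 children, three visits and exposure constant within child, simulated error rates are 13%, 17% and 21% at ρy = 0.3, 0.5 and 0.7. When exposure varies only within child they are 2% or less.

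**Step 4. One visit per child per season.** Then m = 1 and V = 1, so there is no within-child problem. A child with five usable visits would contribute two and leave three unused.

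**The case against.** The strongest reply is that the plan nowhere says visits are pooled. Its wording also fits one visit per child per season, and then linear regression raises no within-child issue. That stands: a reader might infer that repeated visits are treated as independent rows, but the text is silent. Under the one-visit reading the complaint becomes one of efficiency, plus the open question of which visit is used.

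A reader might also infer that every Option 2 child has at least three visits in one season. The documents do not support that. Section T allows 15% attrition, telephone follow-up leaves lung function at visits 1 and 2 only, and visits 1 and 5 may belong to different years' seasons.

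Nor do the documents show that standard errors must be too small. Air quality is taken on the visit date and the preceding days, so it can vary a good deal within a child, and the table shows that ordinary standard errors can then be about right or too large. Against this, the predictors are neighborhood indices and the Aim 4 hypothesis expects exposure to differ with social vulnerability, which makes some positive correlation plausible. Stratifying into two vulnerability levels need not remove it. The direction is still not settled.

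Four smaller objections also stand. The plan mentions no cross-validation folds, so leakage between folds is only a possibility. Nothing says that visit 2 enters Aim 4, and the latent transition analysis and the quality-of-life model both leave it out. Exacerbation rate is naturally one value per child per period, so the visit count does not bear on it directly. Finally, Aim 4 is supplemental and labelled exploratory. That label, however, explains the absence of multiplicity adjustment; it does not deal with correlated rows.

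**Conclusion.** The point holds as a gap in specification with a quantifiable consequence. Aim 4 names only linear regression, does not say which visits enter, and gives no method for within-child correlation, although the same section names suitable methods for other repeated outcomes. If visits are pooled, the stated 0.05 is not assured: the actual rate runs from well below 5% (exposure varying only within child), through about 5-6% (uncorrelated exposure), to about 19% (exposure constant within child). If one visit per season is meant, data already collected are set aside.

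These rates rest on assumed values for the number of children, visits per child and outcome correlation; the visit counts rest on assumed half-year seasons. The consequence is confined to an exploratory, supplemental aim, but a child-level model is the better choice under either reading and is cheap to specify.

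**What to change.** In the Aim 4 text of Section U:

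- State which visits and contacts are eligible for each season's model, and whether a season is a label across years or one continuous period.
- For outcomes measured at visits, replace linear regression with a linear mixed model with a random intercept per child, or GEE with child-clustered standard errors, using all eligible visits in the season. Apply the same to Option 1 children's repeat questionnaires.
- Exclude visit 2 from Aim 4, or give it its own indicator.
- If ElasticNet is tuned by cross-validation, keep all visits of a child in one fold.

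Standard errors clustered by area should not be added unless the area unit and the number of areas support them; the documents give neither.

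The cost is a few sentences in the plan and somewhat more programming, with no new data. Where exposure is mainly at neighborhood level, confidence intervals will be wider than ordinary regression on pooled visits would report.

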Through supplemental funding, the study team will also test the central hypothesis that climate change-induced disruptions in air quality worsen asthma inflammation, symptoms, and longitudinal outcomes in school-age children with asthma and that these effects are mediated by social vulnerability. Two additional aims to be pursued are below:

**Aim 4. Determine associations between climate, air quality, symptoms, and outcomes in children with exacerbation-prone asthma during two climate seasons.**

Hypothesis: Children with greatest social vulnerability will have more air pollution exposure, increased symptoms, poorer lung function, more exacerbations and decreased QOL during each season.

**Aim 5. Determine the biological impact of climate and pollutants in children with exacerbation prone asthma.** Children with greatest social vulnerability and the highest air pollution exposure will have differentially expressed cytokines and metabolomic features.

This project involves a multidisciplinary team with a history of collaboration and is aligned with the NINR Strategic Plan to “*Advance Symptom Science Research*” in chronic conditions through biobehavioral research. The study population, children with exacerbation-prone asthma, has also been understudied in this regard. This project is expected to: 1) refine knowledge regarding the identification and clinical utility of symptom clusters in these children, and 2) identify mechanisms underlying symptom clusters that can be targeted in future interventional studies, to reduce the high morbidity and improve quality of life.

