### **Option 1: A single study visit with telephone/email and electronic medical record follow-up for up to 48 weeks**

Visit 1 (enrollment) will involve informed consent and participant characterization for the purpose of symptom cluster identification. After this visit is completed, the participant's medical record will be reviewed for up to 48 weeks to assess for asthma exacerbations requiring medical treatment. Telephone/email contacts will also be attempted at 24 weeks and 48 weeks after this visit to ensure that asthma exacerbations treated outside of a healthcare facility or other asthma exacerbations that are managed at home are accounted for.

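### Aim 4 relates exacerbation rates accrued over a season to air quality on only six days around a visit, and does not define the period over which exacerbations are counted

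*Combined protocol and SAP*

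**What the plan says.** Section U, in the plan for the supplemental aims, takes neighborhood air quality indices as predictors. Its outcomes are asthma control and symptoms, lung function, and "exacerbation rates and QOL (outcome variables) during two separate seasons". The Aim 4 hypothesis in Section B has the same time frame: the most socially vulnerable children are expected to have "more exacerbations and decreased QOL during each season".

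On the model, Section U states: "Prespecified outcomes are continuous and will be evaluated with linear regression". Analyses are stratified by season and social vulnerability. On exposure timing it says only this: "Models will be generated for air quality variables on the visit date and for each of the five lag days prior to the visit". No separate exposure window is given for exacerbations.

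Exacerbations are collected over months. For Option 1, which has a single study visit, Section I states: "After this visit is completed, the participant's medical record will be reviewed for up to 48 weeks". It adds: "Telephone/email contacts will also be attempted at 24 weeks and 48 weeks after this visit". Option 2 participants give a medical history at weeks 0, 2, 16, 32 and 48 (Section K). Section U gives no season dates and no counting interval for the Aim 4 rate. It does not say which visit anchors the exposure.

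**The concern.** A visit-day and short-lag exposure suits an outcome measured at that visit, such as the asthma control score, symptoms or spirometry. An exacerbation rate is a different kind of quantity, because it sums events over weeks or months. If the plan is followed as written, each child's rate is regressed on air quality from six days that make up a very small part of the time in which the events occurred.

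What is at stake is whether the exacerbation part of Aim 4 can be interpreted. An association, or its absence, would not show whether children exposed to worse air over the season had more exacerbations in it. Because the counting interval is also undefined, two analysts could build the rate in different ways and reverse the order of exposure and outcome.

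**Working it through.** The plan gives no sample size or power figure for Aim 4, so there is no stated figure to reproduce. The check is arithmetic on time windows.

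**Inputs**
- Exposure window: visit day plus five lag days = 6 days (Section U).
- Option 2 visits at weeks 2, 16, 32 and 48 (Section K), giving intervals of 14, 16 and 16 weeks after visit 2.
- Option 1 contacts at 24 and 48 weeks, with record review for up to 48 weeks (Section I).
- Season length: 182 days. This is an assumption (two seasons splitting the year); the documents do not state it.
- For the time-order shares only: events spread evenly over the window (assumption).

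**Share of the counting window covered by the exposure = 6 / L**

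| Counting window | L (days) | 6 / L |
|---|---|---|
| Visit 2 to 3 (14 weeks) | 98 | 6.1% |
| Visit 3 to 4, or 4 to 5 (16 weeks) | 112 | 5.4% |
| Option 1 contact interval (24 weeks) | 168 | 3.6% |
| Season (assumed) | 182 | 3.3% |
| Full follow-up (48 weeks) | 336 | 1.8% |

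**Order of exposure and events under each possible count**

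1. *Counted back from a visit.* The share of events before the exposure window is (L − 6) / L: 92/98 = 93.9%, 106/112 = 94.6%, 176/182 = 96.7%. The exposure comes after nearly all events.
2. *Counted forward from visit 1, as Option 1 events are collected.* The share before the exposure window is 0%. The order is right, but six days are related to events up to 48 weeks later. Of a full 336 days, 336 − 182 = 154 lie outside any one 182-day season, so the count also mixes seasons.
3. *Counted over the whole season, with the visit on day t and every day equally likely.* Averaging over t = 1 to 182:
   - before: (sum of max(t − 6, 0)) / 182² = 15,576 / 33,124 = 47.0%
   - inside: (sum of min(t, 6)) / 182² = 1,077 / 33,124 = 3.3%
   - after: (sum of (182 − t)) / 182² = 16,471 / 33,124 = 49.7%

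   More than half the events precede the exposure window only if (t − 6) / 182 > 0.5, that is from day 98 onward: 85 of 182 possible visit days, or 46.7%.

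The order of exposure and events therefore changes with the counting rule. The low coverage does not: it is between about 2% and 6% throughout.

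**The case against.** **The time order is not shown to be wrong.** A reader might infer that the exposure falls after most of the exacerbations and so cannot have caused them. The documents do not support that as a general statement. Option 1 events are collected after the only study visit, so the exposure precedes all of them. For Option 2, no section says that the Aim 4 rate is counted back from a visit. This objection stands: reversed order is one possible reading, not an established fact.

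**Calendar coverage is not exposure error.** A reader might also infer that exposure is almost entirely misclassified and that the analysis would usually return a null. Neither can be derived. If differences between neighborhoods persist over time, six days could partly stand in for longer exposure; if day-to-day variation dominates, they could not. The documents give no exposure variance, autocorrelation or seasonal exacerbation rate to decide between these. This stands as a limit on what can be claimed about bias. It does not justify the method, because the plan does not present visit-day values as a proxy for seasonal exposure. Children are also seen on different dates over several enrollment years (Section V), so visit-day values mix calendar day with neighborhood.

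**The aim is exploratory.** Section U uses that label to explain why multiple tests are not adjusted for. Exacerbation rate is one of several outcomes in a supplement-funded aim, and the primary and secondary outcomes in Section J are untouched. This limits how much the point matters, but an exploratory label does not align the exposure with the outcome.

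**It is only missing detail.** Partly so, since the counting interval is missing. The exposure window, however, is stated, and it applies to this outcome.

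**Conclusion.** The point holds as a mismatch between a stated exposure window and one named outcome, made worse by an undefined counting interval. Six days of air quality cover about 3% of a season, 5-6% of a 14-16-week visit interval and about 2% of 48 weeks. Under none of the three counting rules examined is that exposure aligned with the rate. The season figure rests on the assumed 182 days, and the time-order shares also rest on evenly spread events; the visit-interval and 48-week coverage figures come directly from the schedule. The direction and size of any bias cannot be computed from the documents. The visit-day and lag models are not in question for asthma control, symptoms and lung function measured at the visit.

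**What to change.** In Section U, in the Aim 4 plan:

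- Keep the visit-day and lag 1-5 models for asthma control, symptoms and lung function measured at the visit.
- For exacerbation rates, state the interval within each season over which events are counted, and how it is set for Option 1 and Option 2 participants.
- Use mean neighborhood air quality over that same interval as the predictor for this outcome.
- An event-date analysis (case-crossover with lags before onset) may be added as a supplement, only for events with a recorded onset date. The documents do not say that onset dates are recorded, and home-managed events may be learned of only at the 24- or 48-week contact. Self-matching also removes the between-child contrast that the Aim 4 hypothesis concerns, so this should not replace the interval-mean analysis.

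The cost is plan wording and linkage of air-quality data over longer intervals. An interval mean smooths short-term peaks, which is a real loss if brief episodes drive exacerbations. No new participant procedures are needed.

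### Aim 4 assumes a 0.05 type 1 error for pollutants chosen by ElasticNet, with no hold-out or post-selection step; if they are tested on the same children, that level does not hold for the selected variables

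*Combined protocol and SAP*

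**What the plan says.** All of this is in section U, under the plan for supplemental R01 funding (aims 4-5).

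- Model: "Prespecified outcomes are continuous and will be evaluated with linear regression". The outcomes are listed as "patient-reported asthma control and symptoms, lung function, exacerbation rates and QOL (outcome variables".
- Strata: "vulnerability (high versus low-to-intermediate) and season (spring/summer versus fall/winter".
- Exposure days: "Models will be generated for air quality variables on the visit date and for each of the five lag days prior to the visit".
- Selection: "Given the relatively small number of participants and high number of air quality predictor variables", the plan says, "we will use ElasticNet to select the most important variables in Python". Variables correlated above 0.8 "will be removed to minimize redundancy".
- Error rate: "Analyses will assume a type 1 error rate of 0.05 without adjustments for multiple testing (exploratory study".

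The section also plans to consider covariates (age, asthma medications, tobacco smoke exposure), to fit models by sex, and to repeat analyses in the second season as a check on temporal stability. It does not give the number of candidate pollutants, the stratum sizes, the penalty or the rule for tuning it. It does not say whether selected variables are refitted in an unpenalised regression. No sample split, hold-out set, permutation or selective-inference method is described.

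**The concern.** ElasticNet looks at the outcome when it decides which pollutants to keep. A regression p-value is calibrated for a variable named before the outcome was seen. Selecting and testing on the same children therefore gives p-values that are too small and intervals that sit too far from zero.

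Waiving multiplicity adjustment tells the reader that many tests were run, each valid at 5%. It does not say that each test on a selected variable has lost its 5% level.

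Aim 4 is meant to show whether pollution and social vulnerability go together with worse asthma outcomes. Pollutants that appear by chance in one vulnerability stratum could be reported as evidence of differential harm.

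**Working it through.** **The plan's own figure.** The only figure is the assumed 0.05. It cannot be reproduced, because the plan gives too few inputs to calculate a realised error rate.

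**The quantity that matters.** For a pollutant j named in advance and with no effect, P(p_j < 0.05) = 0.05. After selection on the same data, the relevant quantity is

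P(p_j < 0.05 | j selected) = P(p_j < 0.05 and j selected) / P(j selected).

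Selection favours variables with a large sample association, so this exceeds 0.05. The size of the excess has to be simulated.

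**Inputs.**

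- Children per model: not stated for Aim 4. Section T gives 173 enrolled and 147 after 15% attrition. Assuming equal strata, 173/4 ≈ 43 and 147/2 ≈ 74; a further run went up to 173/2 ≈ 86.
- Candidate pollutants: the plan says only that the number is high. Assumed 6, 10 and 20.
- Correlation: pairs above 0.8 are pruned. Assumed equal pairwise correlation of 0, 0.3 and 0.6.
- Tuning: not stated. Assumed mixing parameter 0.5 and penalty chosen by five-fold cross-validation.
- Test: not stated. Assumed ordinary least squares on the selected variables, two-sided, without covariates.

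**Simulation.** There were 400 data sets per setting, with the outcome independent of every pollutant. The cells show the share of selected coefficients with p<0.05, on the same data / on fresh data for the same variables.

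| Children | Pollutants | r = 0 | r = 0.3 | r = 0.6 |
|---|---|---|---|---|
| 43 | 6 | 0.291 / 0.053 | 0.272 / 0.038 | 0.230 / 0.044 |
| 43 | 10 | 0.335 / 0.052 | 0.263 / 0.057 | 0.265 / 0.057 |
| 43 | 20 | 0.393 / 0.057 | 0.317 / 0.057 | 0.264 / 0.045 |
| 74 | 6 | 0.307 / 0.048 | 0.307 / 0.052 | 0.235 / 0.065 |
| 74 | 10 | 0.314 / 0.069 | 0.294 / 0.047 | 0.276 / 0.038 |
| 74 | 20 | 0.410 / 0.059 | 0.299 / 0.043 | 0.271 / 0.062 |

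On the same data the range is 23% to 41%. On fresh data it is 3.8% to 6.9%, which is the nominal 5% within simulation error. Only the reuse of the data differs between the two figures. A second simulation (43 to 86 children, 10 to 20 pollutants, r = 0.3) gave 31% to 34% against 5% to 7%.

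**Per-model rate, for comparison.** The share of null models with at least one p<0.05 was 16% to 39% with cross-validated ElasticNet. With all pollutants entered and no selection it was 18% to 62%, and it was higher than the ElasticNet figure in each of the 18 settings.

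**Dependence on the penalty.** The same per-model share was 0 to 2% with the penalty fixed at 1.0, where little is selected, and 22% to 74% with it fixed at 0.2.

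**The case against.** The strongest reply is that the two-step test is inferred. The plan never says that selected variables are refitted by ordinary regression on the same children. The 0.05 sentence follows the sentences on covariates and sex-specific fits, and it says only that the level is assumed. This stands in part: the inference step is unspecified, so the criticism is conditional on a same-data refit. But linear regression is the named method, the 0.05 covers the analyses without exception, and no other data set for testing is described.

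A second reply is that Aim 4 is supplemental and labelled exploratory. That limits the consequences, since neither the primary nor the secondary outcome is affected. It does not restore the stated level.

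A third is the second-season repeat. It is a real but partial safeguard. It re-runs the analyses and is not defined as a test of the first-season selection. Its sentence also follows directly on the optional analyses of dichotomised outcomes, so its scope is unclear.

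A reader might go further and infer that ElasticNet will make a quarter to a third of Aim 4 models show a false pollutant. The documents do not support this. The pollutant count, stratum sizes, tuning rule and refit are all missing. The per-model rate is also higher with no selection at all, so it mostly reflects multiplicity across pollutants, which the plan openly accepts. Nor do the documents fix a number of models: 6 days × 2 vulnerability strata × 2 seasons × 5 outcomes = 120 holds only if the outcome list is counted as five.

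**Conclusion.** The concern holds for the error rate per selected variable. If ElasticNet-selected pollutants are tested by ordinary regression on the same children, 0.05 is not the error rate of those tests. Under the assumed settings (43 to 86 children, 6 to 20 pollutants, correlation 0 to 0.6, five-fold cross-validation), about 23% to 41% of selected null variables reach p<0.05, against about 5% on independent data.

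These figures illustrate the mechanism and do not predict the trial's own rate. The realised rate depends on choices that the plan leaves open, and the simulations had no covariates. The point should be settled before Aim 4 is analysed, but it does not bear on the trial's main conclusions.

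**What to change.** In the Aim 4 plan, remove the 0.05 statement for ElasticNet-selected variables and do one of the following:

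- Report the selected variables with cross-validated performance and selection stability (for example, how often each is chosen across resamples), without nominal p-values. This is the simplest option.
- Obtain p-values by permutation, re-running tuning, selection and regression on each permuted data set. Permute residuals after the planned covariates. Permuting the raw outcome would break its link with age, medications and smoke exposure.

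If confirmation is wanted, fix the first-season selection and test only those variables on second-season data. State that this is not fully independent if the same children contribute to both seasons.

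In either case, state the candidate list, the penalty and tuning rule, the expected stratum sizes and whether a refit is done.

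The cost is computing time, SAP wording and fewer or larger p-values. No new participants or procedures are needed. Splitting the sample within strata is not recommended: 43 children would leave about 21 to select on and 21 to test on, with unstable selection and little power.
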